9.2. Patient surveys

Three separate patient surveys will be administered several times over the course of the study.

9.2.1. *Overactive Bladder Symptom Quality of Life Questionnaire (OABq)*

The OABq is a 33-item questionnaire that measures quality of life. It contains a “symptom bother” subscale and a Health-Related Quality of Life (HRQoL) subscale. Each question is scored using a six-point scale, with higher scores indicating more severe symptoms or poorer

quality of life. The scores are summed separately for the 2 subscales and transformed into 2 composite scores ranging from 0 to 100.

9.2.2. *Patient reported satisfaction assessment*

The patient reported satisfaction assessment will rate each subject's level of satisfaction with the eCoin™ neuromodulation system on a scale of one to five, where one is "Not at all satisfied" and five is "Completely satisfied." The satisfaction assessment will ask the following three questions:

- "How satisfied is the subject with the eCoin device itself?"
- "How satisfied is the subject with the programming of the device?"
- "How satisfied is the subject with the stimulation of the device?"

9.2.3. *Patient Global Impression of Improvement (PGI-I) questionnaire*

The PGI-I questionnaire will assess patient-reported overactive bladder condition on a scale of one to seven. The questionnaire inquires "Compared to how the subject's urinary leakage was before treatment, subject now reports that he or she feels", with responses ranging from one ("Very much better") to seven ("Very much worse").

10. **Efficacy analyses**

10.1. **Primary efficacy analysis**

This open label, single-arm study will evaluate the effectiveness of eCoin™ in reducing episodes of UUI. The primary efficacy outcome is achieving at least a 50% reduction from baseline in the number of UUI episodes per 24 hours on a 3-day voiding diary after 48 weeks of eCoin™ tibial nerve stimulation. The proportion of subjects achieving at least a 50% reduction along with its 2-sided 95% exact Clopper-Pearson confidence interval will be summarized for subjects in the ITT population.

Because this study is investigating an implanted device, nearly all implanted subjects are expected to have data on the primary endpoint. Careful clinical planning that minimizes

subject dropouts will be implemented. Any missing data for the primary outcome will be handled as follows:

- Any subject explanted, except for those explanted for an MRI, prior to 48 weeks post-activation will be imputed as a non-responder (meaning the subject will be imputed as having not achieved at least a 50% reduction from baseline in the number of UUI episodes).
- Subjects who are explanted for an MRI will have data post-MRI imputed. These imputed data for the primary effectiveness outcome variable will be assumed missing at random and will be handled with multiple imputation. See Section 13.2 for further details and example SAS code.
- Any subject for whom 48 week post-activation data are unavailable and the study investigator does not know whether the device has been explanted will be assumed to be a non-responder.
- Subjects for whom 48 week post-activation data are unavailable but the device is known not to have been explanted will have their missing data imputed. The missing data for the primary effectiveness outcome variable will be assumed missing at random and will be handled with multiple imputation. See Section 13.2 for further details and example SAS code.
- Any subject who undergoes a procedure for implantation of eCoin™, whether or not the device is activated, will be treated as if they were activated.

10.2. Key secondary efficacy analysis

The key secondary effectiveness outcome is achieving at least a 50% reduction from baseline in the number of UUI episodes per 24 hours on a 3-day voiding diary after 24 weeks of eCoin™ tibial nerve stimulation. The proportion of subjects with at least 50% reduction from baseline along with its 2-sided 95% exact Clopper-Pearson confidence interval will be summarized for subjects in the ITT population.

Any missing data for the key secondary efficacy outcome will be handled the same as missing data for the primary outcome.

10.3. Secondary efficacy analyses

The secondary efficacy outcomes will be based on data after both 24 and 48 weeks from device activation. The analyses will be done for the ITT population, unless otherwise specified.

The proportion of subjects achieving a 75% improvement from baseline in the number of UUI episodes per 24 hours on a 3-day voiding diary will be summarized along with its 2-sided 95% exact Clopper-Pearson confidence interval. The proportion of subjects achieving dryness (100% improvement from baseline in UUI episodes) will be summarized along with its 2-sided 95% exact Clopper-Pearson confidence interval. Any missing data for either analysis will be handled the same as missing data for the primary outcome.

The change from baseline will be summarized with descriptive statistics (n, mean, median, standard deviation, 25th quartile, 75th quartile, minimum, and maximum) for the following measures per 24 hours on a 3-day voiding diary. Boxplots with observed values and change from baseline may also be presented. Missing data will not be imputed for these analyses.

- Number of urgency urinary incontinence episodes
- Number of urinary voids (for subjects in the ITT population whose baseline value is more than 10 voids per day)
- Number of urgency episodes
- Number of nocturia episodes

The change from baseline in OABq score will be summarized with descriptive statistics. Boxplots with observed values and change from baseline may also be presented. OABq scores will be presented by subscale composite score (symptom bother and Health-Related Quality of Life). Missing data will not be imputed for these analyses.

Observed scores for the patient reported satisfaction assessment and PGI-I questionnaire will be summarized with descriptive statistics. Boxplots with observed values may also be

presented. Missing data will not be imputed for these analyses. The scores for the three-question patient reported satisfaction assessment will be presented by question.

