The primary effectiveness outcome is achieving at least a 50% reduction from baseline in the number of urgency urinary incontinence episodes per 24 hours on a 3 day voiding diary after 48 weeks of eCoin[™] tibial nerve stimulation.

The proportion of responders along with its 2-sided 95% exact Clopper-Pearson confidence interval will be summarized after 48 weeks of therapy.

3-9-3-3-2 Key Secondary Effectiveness Outcome

The key secondary effectiveness outcome is achieving at least a 50% reduction from baseline in the number of urgency urinary incontinence episodes per 24 hours on a 3 day voiding diary after 24 weeks of eCoin[™] tibial nerve stimulation.

Pivotal Study of Subcutaneous Tibial Nerve Stimulation with eCoin[®] for Urgency Urinary Incontinence.

The proportion of subjects with at least 50% reduction from baseline along with its 2-sided 95% exact Clopper-Pearson confidence interval will be summarized after 24 weeks of therapy.

3-9-3-3-3 Primary Safety Outcome

The primary safety outcome is device-related adverse events from implantation to 52 weeks after implantation of eCoin[™].

All device-related adverse events up to 52 weeks after implantation of eCoin[™] will be summarized by preferred term. Tabulations of these data will include the number of subjects exposed and the number of subjects with at least one device-related adverse event.

3-9-3-3-4 Key Secondary Safety Outcome

The key secondary safety outcome is device-related adverse events 28 weeks after implantation of eCoin[™].

All device-related adverse events up to 28 weeks after implantation of eCoin[™] will be summarized by preferred term. Tabulations of these data will include the number of subjects exposed and the number of subjects with at least one device-related adverse event.

3-9-3-3-5 Secondary Outcomes

The secondary outcomes listed in this section are based on data after 24 and 48 weeks from activation (28 and 52 weeks after implantation). These outcomes, which are for descriptive purposes, will not be formally analyzed statistically. The SAP will describe in detail analyses of the secondary outcomes.

- Achieving 75% improvement in the number of urgency urinary incontinence episodes per 24 hours on a 3 day voiding diary.
- Achieving 100% improvement in urgency urinary incontinence episodes (“Dryness”) per 24 hours on a 3 day voiding diary.
- Reduction from baseline in the number of urgency urinary incontinence episodes per 24 hours on a 3 day voiding diary.

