- Reduction from baseline in the number of urinary voids per 24 hours on a 3 day voiding diary in those subjects whose baseline shows more than 10 voids per day.
- Reduction from baseline in the number of urgency episodes per 24 hours on a 3 day voiding diary.

Pivotal Study of Subcutaneous Tibial Nerve Stimulation with eCoin[®] for Urgency Urinary Incontinence.

- Reduction from baseline in the number of nocturia episodes per 24 hours on a 3 day voiding diary.
- Change from baseline in patient-reported quality of life utilizing the Overactive Bladder Symptom Quality of Life Questionnaire (OABq).
- Change from baseline in patient-reported overactive bladder condition utilizing the Patient Global Impression of Improvement (PGI-I) questionnaire.
- Patient-reported satisfaction with eCoin[™] therapy utilizing the custom patient satisfaction rating survey.

3-9-3-4 Exploratory Subgroup Analyses

Subjects who respond to treatment (i.e., who achieve at least a 50% reduction from baseline to 48 weeks post-activation in the number of urgency urinary incontinence episodes per 24 hours on a 3 day voiding diary) will be compared to non-responders in terms of baseline characteristics, demographics, and effectiveness endpoints.

3-9-4 Sample Size Consideration

The study is designed to estimate the proportion of subjects achieving a clinically meaningful level of improvement, defined as subjects with at least a 50% reduction from baseline in the number of urgency urinary incontinence episodes after 48 weeks of therapy. Up to 135 subjects will be enrolled, with a target enrollment of 120 subjects. The performance goal for this study is to show at least a 40% response rate after 48 weeks of therapy. The primary efficacy analysis will be performed by testing the null hypothesis H_0 that the percentage responding is less than or equal to 40% against the alternative hypothesis H_1 that the percentage is greater than 40%. The test will be performed at an overall 1-sided 2.5% level of significance.

H_0 : the true percentage responding $\leq 40\%$

H_1 : the true percentage responding $> 40\%$

The study will be considered successful if the lower bound of the 2-sided 95% exact Clopper-Pearson confidence interval for the percentage responding is greater than 40%.

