Objective: to assess safety 52 weeks after implantation of eCoin™
Outcome: device-related adverse events from implantation to 52 weeks after implantation of eCoin™

Key secondary safety
Objective: to assess safety 28 weeks after implantation of eCoin™
Outcome: device-related adverse events from implantation to 28 weeks after implantation of eCoin™

Secondary
The following secondary objectives and outcomes will be based on data after both 24 and 48 weeks from activation:
Objective: to evaluate the effectiveness of eCoin™ with respect to the following outcome measures:

- Proportion of subjects achieving 75% improvement in the number of UUI episodes per 24 hours on a 3-day voiding diary
- Proportion of subjects achieving 100% improvement in the number of UUI episodes per 24 hours on a 3-day voiding diary
- Change from baseline in the number of UUI episodes per 24 hours on a 3-day voiding diary
- Change from baseline in the number of urinary voids per 24 hours on a 3-day voiding diary in those subjects whose baseline shows more than 10 voids per day
- Change from baseline in the number of urgency episodes per 24 hours on a 3-day voiding diary
- Change from baseline in the number of nocturia episodes per 24 hours on a 3-day voiding diary
- Change from baseline in patient-reported quality of life utilizing the Overactive Bladder Symptom Quality of Life Questionnaire (OABq)
- Change in patient-reported overactive bladder condition utilizing the Patient Global Impression of Improvement (PGI-I) questionnaire
- Patient-reported satisfaction with eCoin™ therapy utilizing the custom patient satisfaction rating survey

4. Study schedule

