7.2. Baseline

Baseline efficacy measures will be defined as the last measure taken up to and including the baseline visit (Visit 2). Baseline safety measures will be defined as the last measure taken prior to device implantation.

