8.5. Concomitant therapy

A concomitant therapy is defined as therapy (other than eCoin™) started on or after implantation. A therapy taken prior to implantation is not considered a concomitant therapy. If a subject stops taking or changes the dosage of a medication recorded in the medical history at screening, or begins taking a new medication, then this medication will be included as a concomitant medication. Information on concomitant medications will be summarized by generic name as reported on the concomitant medication CRF.

The number and percentage of subjects who took at least one drug within each generic type will be presented. Concomitant medications will be presented separately for OAB and non-OAB medications.

9. Follow-up assessments

9.1. 3-day voiding diary assessments

Throughout the study, subjects will complete 3-day voiding diaries to quantify voiding behavior, symptoms, and incontinence. The diary should be completed over three consecutive days during the seven days prior to each visit involving a 3-day diary. The site should telephone subjects to remind them of the diary requirement at least three days prior to each visit. The voiding diaries will collect the following information per 24 hours over 3 days:

- total number of daytime voids (6:01 a.m. – 9:59 p.m.)
- total number of night voids (10:00 p.m. – 6:00 a.m.)
- total number of voids
- total amount voided
- total number of toilet urgent episodes
- total number of leaks
- total amount leaked
- total number of urge leaks

The voiding diary CRF will report the total over the three days for each measure, which will then be averaged. All efforts will be made to ensure that all diaries are completed over the full three day period. Any incomplete diaries will be reported and averaged over the total days in which they were completed.

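### Change in voids is summarised only in subjects selected on the same baseline diary value that is then subtracted, so some fall is expected even without a treatment effect; an all-ITT row and a footnote should be added.

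*SAP*

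**What the plan says.** The restriction is stated consistently. SAP 10.3 gives the measure as "Number of urinary voids (for subjects in the ITT population whose baseline value is more than 10 voids per day". SAP Table 1 (Section 3) has "Change from baseline in the number of urinary voids per 24 hours on a 3-day voiding diary in those subjects whose baseline shows more than", with the same threshold. Protocol 3-5-2 and Protocol 3-9-3-3-5 likewise define the outcome "in those subjects whose baseline shows more than 10 voids per day".

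The value used for selection is the value used for change. SAP 7.2 states: "Baseline efficacy measures will be defined as the last measure taken up to and including the baseline visit (Visit 2"). SAP 9.1 describes how it is formed: "The voiding diary CRF will report the total over the three days for each measure, which will then be averaged".

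There is no comparison group. SAP 10.1 begins: "This open label, single-arm study will evaluate the effectiveness of eCoin™ in reducing episodes of UUI". For this measure SAP 10.3 plans only that "The change from baseline will be summarized with descriptive statistics", without imputation and without any adjustment for the baseline selection. Protocol 3-9-3-3-5 says of the secondary outcomes: "These outcomes, which are for descriptive purposes, will not be formally analyzed statistically".

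The other diary counts in SAP 10.3 (UUI, urgency and nocturia episodes) are summarised without a baseline cut. SAP 10.4 repeats the secondary analyses in other populations but does not lift the void threshold.

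**The concern.** A 3-day void average is a noisy reading of a subject's usual frequency. A cut at 10 lets in some subjects whose usual frequency is lower but who had a high diary, and leaves out some whose usual frequency is higher but who had a low one. At follow-up the first kind tend to fall and the second to rise, whatever the device does. The planned table reports only the group expected to fall.

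Nothing else in the plan separates this from a device effect. The diary entry criterion (Protocol 3-3-2-2-1, item 3) concerns UUI episodes and sets no minimum number of voids, so the cut at 10 is a further selection. The other pre-implant diary is kept during the last three days of TENS (SAP 2.4) and falls after the Visit 2 baseline, so it is not an untreated second baseline. Each repeat under SAP 10.4 carries the same cut.

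At stake is how one descriptive figure is read, in a study meant to support a Pre-Market Approval Application (Protocol 3-1). A reader who takes the mean fall in voids as the device's effect would credit it with some fall that comes from the selection.

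**Working it through.** **Plan's own figure.** None. Neither document gives a baseline void mean, an SD, a diary-to-diary correlation or an expected change.

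**Inputs from the documents.** Cut: more than 10 voids per day (SAP 10.3). The same Visit 2 value selects and is subtracted (SAP 7.2). No control arm (SAP 10.1).

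**Inputs assumed.** Mean *m*, SD *s*, correlation *r* between two 3-day diaries, roughly normal values, no treatment effect, and no drift in the whole group.

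**Formula.** With a = (10 − m)/s and λ = φ(a)/(1 − Φ(a)), the mean baseline of the selected group is m + sλ. Its expected follow-up is m + r·sλ. The expected fall is therefore

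(1 − r) × s × λ,

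which is zero only if r = 1.

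**Central illustration, m = 11, s = 3.**
- a = (10 − 11)/3 = −0.333; φ(a) = 0.377; 1 − Φ(a) = 0.631, so about 63% of subjects exceed 10.
- λ = 0.377/0.631 = 0.598; sλ = 1.80; mean baseline of the subset 12.80.
- r = 0.9: 0.1 × 1.80 = 0.18 voids/day.
- r = 0.8: 0.2 × 1.80 = 0.36.
- r = 0.7: 0.3 × 1.80 = 0.54.

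**Range.**

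| Assumed mean | SD | r | Share above 10 | Expected fall |
|---|---|---|---|---|
| 12 | 2.5 | 0.9 | 79% | 0.09 |
| 12 | 3 | 0.7 | 75% | 0.38 |
| 10 | 3 | 0.7 | 50% | 0.72 |
| 9 | 4 | 0.7 | 40% | 1.16 |

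So means of 9 to 12, SDs of 2.5 to 4 and r of 0.7 to 0.9 give 0.09 to 1.16. Extending to means up to 13 and r down to 0.5 widens this to 0.05 (mean 13, SD 2.5, r 0.9) and 1.93 (mean 9, SD 4, r 0.5). Every case with r below 1 is a fall.

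**Check by simulation.** 400,000 subjects, gamma-distributed personal means averaging 11, two diaries rounded to thirds of a void, no treatment effect, no selection on UUI episodes:

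| r | Above 10 at baseline | 10 or below | All |
|---|---|---|---|
| 0.86 | falls 0.25 | rises 0.38 | 0.00 |
| 0.73 | falls 0.52 | rises 0.77 | 0.00 |

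About 60% of subjects are above the cut in both runs, so the fall and the rise cancel (for example 0.60 × 0.25 ≈ 0.40 × 0.38 ≈ 0.15). The zero in the last column shows what removing the void cut does on its own. It does not predict the trial's ITT change, because ITT subjects are also selected on UUI episodes.

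**The case against.** **It is pre-specified and only descriptive.** The restriction reads the same in both documents and was not chosen after seeing data. No test, success rule or power figure depends on it. All of this stands, and limits the point to a low-priority improvement. It does not remove the selection effect, which pre-specification leaves untouched.

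**Frequent voiders are a sensible group to describe.** This is fair, although the documents give no reason for the value 10. Subjects with few voids have little to gain on this measure and would dilute an all-subject average. The subset should stay as the named outcome; placing an all-ITT row ahead of it would demote that outcome as a matter of preference.

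**The all-ITT row is not clean either.** This stands. Every eligible subject needed at least one UUI episode on each of three days of a baseline diary. If voids and UUI episodes move together within a diary (no figure is given), the all-ITT void change will also regress somewhat. Nor does the gap between the two rows measure the bias, since frequent voiders may truly respond differently. The extra row reduces the problem without removing or measuring it.

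**The size is unknown.** This stands. The range comes wholly from the assumptions, and the effect is trivial if most subjects exceed 10 voids and diaries repeat well.

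**Void data appear elsewhere.** Protocol 3-9-5 describes measuring frequency at every follow-up visit without the cut, and voids enter the imputation model (SAP Table 3). Neither commits to an all-ITT summary of change, so this answers the point only in part.

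**Conclusion.** The point holds as an inexpensive improvement to one descriptive secondary outcome. Followed exactly, the plan reports a change in voids that leans toward improvement whenever diary-to-diary correlation is below 1 and the group mean does not otherwise drift. For illustration only, the lean is 0.2 to 0.5 voids per day at mean 11, SD 3 and r 0.7 to 0.9, and about 0.1 to 1.2 over the wider assumptions above.

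Three stronger readings are not supported:
- A reader might infer that the trial's main result is inflated by this cut. It is not: the primary and key secondary responder outcomes carry no void threshold, and the sample size and type I error do not depend on this measure.
- A reader might infer that the all-ITT change would be an unbiased estimate of effect. It would still be uncontrolled and selected on baseline UUI episodes.
- A reader might infer that the documents contradict themselves or that the bias is known to be large. The restriction is consistent throughout, and the documents contain nothing from which its size can be derived.

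**What to change.** In SAP 10.3, keep the more-than-10 subset as the named outcome and add beside it the same descriptive statistics of change in voids for all ITT subjects, at weeks 24 and 48. Add a footnote with two statements: the subset was selected on the baseline value from which its change is computed and is subject to regression to the mean; and the all-ITT row lacks the void cut but is uncontrolled and selected on baseline UUI episodes.

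The cost is small: one row at each of two visits, carried through the SAP 10.4 repeats if wanted, and a footnote. No new data are needed, because the diaries already record voids at baseline and every follow-up assessment. SAP 7.3 provides for a documented revision before database lock. The objectives and outcome lists in the protocol and SAP Table 1 can stand as written, and a supplementary descriptive row does not appear to alter a principal feature of the protocol, which is the trigger for an amendment in Protocol 3-9-3.

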10.4. Sensitivity and additional analyses

The primary and secondary efficacy analyses will be repeated for all analysis populations (mITT, OAB drug-free, Per-protocol, Responders, and TENS cohort analysis). These analyses will also be repeated for the mITT analysis population excluding any subjects enrolled but not meeting all eligibility criteria who were subsequently re-baselined to correct any eligibility violations.

Additional sensitivity analyses may be conducted to evaluate different methods of handling missing data, such as tipping point, best-case, and worst-case scenario analyses.

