a. Weight, height, body mass index, temperature, pulse rate, respiratory rate, and blood pressure will be assessed at the screening visit. Only pulse rate, temperature, and blood pressure will be collected at subsequent visits. In addition, respiratory rate will be collected at visit 4 and visit 13.
b. For visits involving a 3-day diary, the diary should be completed over 3 consecutive days during the 7 days prior to each indicated visit. The site should give patients a telephone call to remind them of the diary requirement at least 3 days prior to each follow-up visit.
c. Visit 3 (Implant procedure) will assess satisfaction and impression of improvement relative to the TENS therapy. All other visits will be relative to the eCoin™ neuromodulation device.

5. Analysis populations

Effectiveness analyses will be generated for all analysis populations described below. Safety data will be reported on all enrolled subjects who undergo a procedure for implantation of the study device.

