5.5. Responders

The responders population will include all subjects who respond to treatment, defined as those who achieve at least a 50% reduction in the number of UUI episodes from baseline to 48 weeks post-activation.

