10.4.1. Exploratory subgroup analyses

The proportion of subjects who respond to treatment (achieve at least a 50% reduction from baseline in the number of UUI episodes per 24 hours on a 3-day voiding diary after 48 weeks of eCoin™ tibial nerve stimulation) will be summarized for various subgroup populations based on baseline characteristics, demographics, and effectiveness endpoints. For each subgroup, a forest plot will show the proportion of responders along with its 95% confidence interval. A logistic regression may also be used to describe the relationship between response to treatment and different subgroup populations.

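### Repeating the primary analysis in the Responders set returns 100% by definition, and SAP 10.4.1 appears to use post-treatment outcomes as subgroup factors for response

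*SAP*

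**What the plan says.** SAP 5.5 gives the membership rule for the Responders set: "defined as those who achieve at least a 50% reduction in the number of UUI episodes from baseline to 48 weeks post-activation". SAP 10.1 defines the endpoint: "The primary efficacy outcome is achieving at least a 50% reduction from baseline in the number of UUI episodes per 24 hours", assessed after 48 weeks of stimulation. The event and the visit are the same.

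SAP 10.4, headed as sensitivity and additional analyses, then says: "The primary and secondary efficacy analyses will be repeated for all analysis populations (mITT, OAB drug-free, Per-protocol, Responders, and TENS cohort analysis". Protocol 3-9-7 carries the same sentence. The opening of SAP section 5 is broader still: "Effectiveness analyses will be generated for all analysis populations described below". Protocol 3-9-3-2 agrees, and Responders is on both lists. Neither document exempts the primary endpoint.

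SAP 10.4.1 summarises week-48 response in "various subgroup populations based on baseline characteristics, demographics, and effectiveness endpoints", with forest plots and possibly logistic regression. It names no endpoint, visit or cut-point. Protocol 3-9-3-4 runs the other way: it compares responders with non-responders on the same three kinds of variable.

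The success rule (SAP section 6) requires the lower limit of the exact 95% Clopper-Pearson interval to exceed 40%. SAP 5.1 and 10.1 place the primary analysis in the ITT population.

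**The concern.** A sensitivity analysis is useful only if it could have come out differently. A responder rate computed among people chosen because they responded cannot. It would still be tabulated with an exact interval, beside repeats in the mITT, drug-free, per-protocol and TENS sets that can vary. A reader scanning the row of estimates would see one that clears the performance goal by a wide margin and says nothing about the device.

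The subgroup plan raises a related problem. If week-48 response is plotted or regressed against outcomes measured during treatment, the display shows that outcomes agree with each other. It does not show which patients are likely to benefit, because those factors are unknown when treatment is chosen.

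**Working it through.** 1. **The plan's own figure.** For x responders among n, the Clopper-Pearson limits are the 2.5th percentile of Beta(x, n − x + 1) and the 97.5th percentile of Beta(x + 1, n − x). For 60/120 this gives 40.7% to 59.3%, matching (0.41, 0.59) in SAP Table 2. For 59/120 the lower limit is 39.9%. So with 120 subjects the ITT analysis succeeds at 60 responders and fails at 59. It can go either way.

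2. **Primary endpoint in the Responders set.** Here x = n = m, the number of responders. The estimate is m/m = 100%, the upper limit is 100%, and the lower limit L solves L^m = 0.025, so L = 0.025^(1/m).

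| ITT result | ITT lower limit | Responders repeat | Lower limit |
|---|---|---|---|
| 24/120 (20%) | 13.3% | 24/24 (100%) | 85.8% |
| 36/120 (30%) | 22.0% | 36/36 (100%) | 90.3% |
| 60/120 (50%) | 40.7% | 60/60 (100%) | 94.0% |

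   The lower limit passes 40% with as few as five responders: 0.025^(1/5) = 47.8%, against 0.025^(1/4) = 39.8%.

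3. **Other endpoints in the Responders set.** These are not the event that defines the set. For example, "The key secondary effectiveness outcome is achieving at least a 50% reduction from baseline in the number of UUI episodes per 24 hours" refers to 24 weeks. They are raised by selection but can vary. The documents give no rate for the 75% threshold and no correlation between visits, so the following are illustrations.
   - Assume 53% respond at week 48 (the rate at which the plan states 80% power) and 20% to 40% of all subjects reach a 75% reduction. Every subject in the latter group is a responder, so among Responders the rate is 0.20/0.53 = 38% to 0.40/0.53 = 75%.
   - Assume 53% respond at each of weeks 24 and 48, with an underlying bivariate-normal correlation of 0.3 to 0.9. Week-24 response among Responders is then 62% to 87%, against 53% overall.

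4. **Effectiveness endpoints as subgroup factors.** The outcome is week-48 response. The strata below are examples, since SAP 10.4.1 names none; the assumptions are those of step 3.

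| Factor | Response in the stratum | Response in the rest |
|---|---|---|
| ≥50% reduction at week 48 | 100% (forced) | 0% (forced) |
| ≥75% reduction at week 48 | 100% (forced) | 41% to 22% |
| ≥50% reduction at week 24 | 62% to 87% | 43% to 15% |

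   For the second row, the rest is (0.53 − q)/(1 − q). With q = 0.20 this is 0.33/0.80 = 41%; with q = 0.40 it is 0.13/0.60 = 22%. Only strata that logically imply response or non-response at week 48 are fixed.

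5. **Which reading of the subgroup phrase.** SAP 10.4.1 lists baseline characteristics and effectiveness endpoints as separate items. If the second meant baseline values, the first would already cover it. The natural reading is therefore post-treatment outcomes. Protocol 3-9-3-4 uses the same list for a descriptive comparison, where outcomes are not made predictors of outcome.

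**The case against.** The best defence is that nothing decisive depends on these outputs. Success rests on the ITT analysis; the subgroup section is headed exploratory; protocol 3-9-3-3-5 calls the secondary outcomes descriptive; and SAP 10.4 covers additional as well as sensitivity analyses. A table labelled Responders that shows 100% response also explains itself. The points about consequence stand and keep this minor. They do not give the primary repeat a purpose. The paragraph in SAP 10.4 that follows the list goes on to further sensitivity analyses, so a reader would take the list as sensitivity work too.

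A second defence is that the subgroup phrase is undefined and could mean baseline values, which would not be circular. The wording does not rule this out, but the separate listing of baseline characteristics makes it the less natural reading. On either reading the text needs to be specific.

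A third is that summaries such as OABq, PGI-I or week-24 status among week-48 responders can be informative. That stands. Only the primary-endpoint repeat is degenerate, so the set need not be abolished.

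A reader might infer that every result in the Responders set, and every effectiveness-endpoint subgroup, is driven to about 100%. The documents do not support that. Steps 3 and 4 show secondary results and week-24 strata well short of 100%, and the complements of the high strata are pushed low. A reader might also infer that the trial's conclusion is inflated. It is not, because the ITT test does not use these analyses.

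**Conclusion.** The point holds as a small, clear defect. The primary analysis repeated in the Responders set gives exactly 100% for any number of responders (60/60, exact 95% interval 94.0% to 100%), including when the ITT analysis fails. This follows from the definitions and assumes only that set membership and the endpoint are scored in the same way. Secondary results in the set are selected on outcome but not fixed; their size depends on the assumed rates and correlations above.

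The subgroup part depends on reading effectiveness endpoints as post-treatment measures. On that reading the analysis conditions on outcome, with forced values only in strata that imply week-48 response or non-response. The ITT primary test, its type I error, its power and the success rule are unaffected.

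**What to change.** Exclude the Responders set from the repeat of the primary-endpoint analysis. The change is needed in SAP 10.4 and in the opening statement of SAP section 5, and likewise in protocol 3-9-7 and 3-9-3-2. Editing SAP 10.4 alone would leave SAP section 5 still requiring the analysis. Label any other Responders summaries as descriptive and selected on outcome. If the set is kept for these, state how membership is decided for subjects whose week-48 outcome is multiply imputed, since it can differ across the 100 datasets.

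In SAP 10.4.1, limit the forest-plot and logistic-regression factors to variables known before activation: demographics, baseline characteristics including baseline UUI frequency, and TENS response, which is recorded before implantation. Describe effectiveness endpoints only by comparing responders with non-responders, as in protocol 3-9-3-4; SAP 10.4.1 does not currently contain that comparison.

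The cost is wording and fewer tables, with no new data, visits or sample size. SAP 7.3 provides for such a revision before database lock. The protocol sentences should be aligned so that the two documents agree.
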